2. Compare the effects of the intervention vs. enhanced usual-care control on secondary outcomes, including short- and long-term changes in diabetes and prediabetes-related outcomes of metabolic markers of glycemic control (a) hemoglobin A1c, and (b) fasting glucose; cardiovascular disease risk factors: (c) fasting lipid profile; and lifestyle outcomes: (d) dietary intake (total energy, simple carbohydrates, saturated fat, number of servings of fruits and vegetables, dietary fibers, and whole grains), and physical activity.
3. Determine the implementation cost of delivering this weight-loss intervention at a Federally Qualified Health Center in the context of a pragmatic clinical trial.

Research Design

This will be a randomized clinical trial testing a weight-loss lifestyle intervention for obese Hispanic women with prediabetes or T2D. The primary aims of the intervention will be to reduce body weight and waist circumference at 6, 12, and 18 months. Secondary aims will be to improve levels of HbA1c, markers of glycemic control (fasting glucose in addition to HbA1c) and cardiovascular disease risk (serum lipid profile), diet, and physical activity. We will also determine the implementation cost for delivering the trial intervention in a federally qualified health center. Following the clinical trial, through a 2-cohort phase, we will assess the sustainability and cost of delivering the intervention as part of regular patient care at the clinic in the absence of research support.

Trial participants will be randomly assigned to one of two conditions: 1) Enhanced usual care control, or 2) a culturally tailored behavioral intervention. Outcome assessments will be conducted at 6, 12, and 18 months. Recruitment will be conducted in seven cohorts of approximately 30 randomized participants each.

Each participant will receive a \$25 gift card at the completion of the 6-month visit, \$30 at 12-month and \$35 at 18-month data collection points.

Eligibility

We will enroll 200 obese Hispanic women in this weight-loss intervention trial.

Inclusion criteria.

- All participants will be patients who receive their primary medical care at the Virginia Garcia Memorial Health Center (VGMHC)
- Self-identified as Spanish-speaking Latina or Hispanic
- Female
- Age 18 and older
- BMI greater than or equal to 27kg/m²
- Classified as diabetic or prediabetic in the electronic medical record by *at least one* of the following:
 - o Fasting plasma glucose ≥ 100

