The change in consent will affect about 90 participants. Participants in the intervention groups will receive their new consent at one of the sessions. Usual care participants will receive a phone call from [name] alerting them to watch for the form in the and if desired discuss the change in the consent.

Prior to randomization, participants will be required to obtain medical clearance for participation from their VGMHC health care provider.

Baseline Data Collection and Randomization

After completing the baseline telephone assessments, participants will be scheduled for a randomization visit at VGMHC. During this visit we will collect baseline measurement of fasting lipids, glucose, and HbA1c as they are done in the course of clinic operations at VGMHC, by

finger-stick using point-of-care devices. Participants will then receive their treatment assignments using a computerized block randomization scheme provided by the study statistician. Randomization will be stratified by baseline BMI (27-34, 35-39, 40 or more) and age (18-45, 46 and above). To ensure equal balance in the two arms, randomization will occur in block sizes of 4. Participants will be informed of their randomization assignments by intervention staff members. Data collection staff will be masked to treatment assignments.

Enhanced Usual Care Control

We considered using a no-treatment control condition, but our community clinic partners requested that we provide the same information to participants in both conditions. This strategy insures that all participants get something they value as part of their involvement in the study, and also provides a comparison of the lifestyle intervention program to a very low-cost and easy to deliver information-only program.

Weight Management Tools for All Trial Participants

So that all randomized participants receive the same basic information, those assigned to the enhanced usual care control condition will receive bilingual printed materials on how to improve weight-related behaviors: copies of the NHLBI “Steps to Lose Weight,” “ChooseMyPlate,” and “Nutrition and Finding Your Way to a Healthier You.” We recognize that literacy limitations may be an issue for some participants, but providing this type of printed material is our approximation of the best current “usual care” practice. In addition to this written material, all participants in both arms of the trial will receive:

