The main analysis will be based on intention-to-treat principles. To test the effect of the intervention on the short term outcomes at 6 months, we will use a residualized change score to determine whether the intervention and control groups differ in change in outcome (e.g., weight and HbA1c) from baseline, controlling for baseline values. The analysis uses regression with the dependent variable being the change in weight (or HbA1c) at 6 months and the independent variables are baseline weight (or HbA1c) and a dummy variable for study arm (intervention versus control). To examine the long-term effect of the intervention we will use multilevel modeling to examine the trajectory of the outcomes across baseline, 6, 12, and 18 months. Weight (or HbA1c) is the dependent variable; time, study arm, and the time by study arm interaction are the independent variables. Quadratic models will be fit to the data, as it is anticipated that the change over time will not be linear throughout the 18 month period. These approaches will also be used for the analysis of the short-term and long-term effects of the intervention on other outcomes: waist circumference, fasting glucose, serum lipid profile, dietary intake (total energy, simple carbohydrates, saturated fat, number of servings of fruits and vegetables, dietary fiber and whole grains), and PA.

Assessment of success in sustainability phase

To evaluate the success of the implementation of the intervention into clinical practice at VGMHC, the average percentage of behavioral strategies, participant objectives, session content completed across sessions, average number of participants recruited, average participant satisfaction, percent of sessions attended in each phase, and average weight change will be reported. These numbers will be compared to the benchmark numbers established during the clinical trial phase of the study.

Additional Analyses

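### The long-term model leaves the baseline difference between arms free, which costs precision at 12 and 18 months: little for weight and waist, more for less correlated secondary outcomes

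*Combined protocol and SAP*

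**What the plan says.** The Statistical Analysis section of the combined protocol and SAP gives two models.

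- **6 months.** Change from baseline is regressed so that "the independent variables are baseline weight (or HbA1c) and a dummy variable for study arm". This is a baseline-adjusted comparison.
- **Long term.** A multilevel model is used to "examine the trajectory of the outcomes across baseline, 6, 12, and 18 months". Its terms are given as: "Weight (or HbA1c) is the dependent variable; time, study arm, and the time by study arm interaction are the independent variables". The time shape is quadratic. No baseline covariate appears, and the arms are not constrained to share a baseline mean.

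The same two approaches serve waist, glucose, lipids, diet and physical activity. Additional Analyses extends the multilevel approach to quality of life and adds only moderators to the models. Under Research Design, "The primary aims of the intervention will be to reduce body weight and waist circumference at 6, 12, and 18 months".

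The Recruitment and Baseline Data Collection and Randomization sections place the weight, waist and blood measurements before the woman receives her assignment. The diet and activity interviews come earlier still.

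**The concern.** Because baseline is measured before assignment, the two arms come from one population with one baseline mean. The long-term model does not use this fact. Its free arm term is an estimate of a quantity known to be zero in expectation, and the change from baseline to 12 or 18 months is measured against that noisy estimate. A chance gap at baseline therefore enters the long-term contrast more fully than it enters the 6-month regression, which adjusts for it.

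At stake is precision in the 12- and 18-month comparisons promised in Aim 1 and Aim 2. The trial is of modest size ("We will enroll 200 obese Hispanic women in this weight-loss intervention trial") and the documents give no power calculation, so there is no stated margin to absorb the loss.

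**Working it through.** **Plan's own figure.** The documents state no power, SD, correlation or covariance structure, so there is no figure to reproduce. I compare the variance of the same contrast with and without a free baseline arm effect.

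**Inputs from the documents.** Visits at 0, 6, 12 and 18 months; quadratic time; two arms in equal balance (blocks of 4); 200 women, so about 100 per arm. The sample size cancels from the ratios.

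**Assumptions.** Equal variances, complete data, arm interacting with both time and time squared (the plan does not say whether the squared term interacts), and within-woman correlation ρ from 0.5 to 0.95. The structure is compound symmetry, or AR(1) with ρ per 6 months.

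**Compound symmetry, by hand.** Work in units of 2σ²/n and fit a quadratic to the arm difference at four equally spaced visits. The only residual direction is (−1, 3, −3, 1)/√20. The fitting weights are therefore h₀₀ = h₁₈,₁₈ = 0.95 and h₀,₁₈ = 0.05.

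- Variance of the fitted baseline difference: 0.95(1−ρ) + ρ = 0.95 + 0.05ρ.
- Variance of the 0-to-18-month contrast, free baseline: (0.95 + 0.95 − 0.10)(1−ρ) = 1.8(1−ρ).
- Covariance of the two: (0.05 − 0.95)(1−ρ) = −0.9(1−ρ).
- Fixing the baseline difference at zero removes the fraction 0.81(1−ρ)² / [(0.95 + 0.05ρ) × 1.8(1−ρ)] = 9(1−ρ)/(19+ρ).

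Putting numbers in: ρ = 0.5 gives 4.5/19.5 = 23%; 0.8 gives 1.8/19.8 = 9%; 0.9 gives 0.9/19.9 = 4.5%; 0.95 gives 0.45/19.95 = 2.3%.

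**All cases, by generalised least squares.** Variance with a common baseline divided by variance with a free baseline:

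| ρ | Compound symmetry, 12 mo | Compound symmetry, 18 mo | AR(1), 12 mo | AR(1), 18 mo |
|---|---|---|---|---|
| 0.5 | 0.655 | 0.769 | 0.558 | 0.564 |
| 0.6 | 0.726 | 0.816 | 0.631 | 0.608 |
| 0.7 | 0.795 | 0.863 | 0.711 | 0.672 |
| 0.8 | 0.864 | 0.909 | 0.799 | 0.756 |
| 0.9 | 0.932 | 0.955 | 0.895 | 0.865 |
| 0.95 | 0.966 | 0.977 | 0.947 | 0.929 |

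At 18 months under compound symmetry, ρ = 0.5 is worth 1/0.769 − 1 = 30% more women and ρ = 0.8 is worth 1/0.909 − 1 = 10%. If only linear time interacts with arm, the 18-month ratios are similar: 0.735, 0.904, 0.954 and 0.977 at ρ = 0.5, 0.8, 0.9 and 0.95.

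**Scale for weight.** Assume an SD of 15 kg, ρ = 0.95, 100 per arm and categorical time. The unadjusted change contrast has SE 15 × √(2 × 0.05) × √(2/100) = 0.67 kg. The adjusted one has 15 × √(1 − 0.95²) × √(2/100) = 0.66 kg. The two estimates differ by (1−ρ) times the chance baseline gap. That gap has SE 15 × √(2/100) = 2.12 kg, so the disagreement has SD 0.05 × 2.12 = 0.11 kg.

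**Baseline as a covariate instead.** With baseline removed from the outcome, three visits remain and a quadratic fits them exactly. Under compound symmetry the contrast variance is then 1−ρ² in the same units. Against the plan's 1.8(1−ρ), the ratio is (1+ρ)/1.8: 0.83 at ρ = 0.5, 1.00 at 0.8, 1.06 at 0.9 and 1.08 at 0.95. At the correlations plausible for weight, this version is 6-8% less precise than the plan.

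**The case against.** The strongest reply is that the planned model is conventional and unbiased, and that the loss hardly touches the primary outcomes. Much of this stands.

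- A reader might infer that the 6-month and long-term analyses contradict each other, or that the long-term one is biased. The documents do not support this. Each model is assigned to its own question, and under randomisation, with complete data and the right mean shape, both estimate the same kind of difference in mean change.
- A reader might infer a serious loss for weight and waist. At ρ of 0.9-0.95 it is 2-5% of variance under compound symmetry. Stratifying by three baseline BMI bands also limits chance imbalance in weight, though less so in lipids or diet.
- The size is assumed throughout, and the two correlation structures give clearly different answers.
- The plan describes a trajectory and a time-by-arm interaction but defines no 12- or 18-month contrast. That is a separate gap. Aim 1 nevertheless promises those comparisons, so their precision is a fair question.

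The direction survives: the free-baseline contrast was never the more precise one in any case computed for the same time shape.

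**Conclusion.** The point holds as an avoidable inefficiency and an inconsistency of method. Under the assumed quadratic-by-arm model, a common baseline mean cuts the 18-month variance as follows:

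- ρ of 0.8-0.5 (plausible for HbA1c, glucose, lipids and diet): about 9-23% under compound symmetry, 24-44% under AR(1).
- ρ of 0.9-0.95 (plausible for weight and waist): 2-5% and 7-14%.

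It is worth correcting mainly for the less correlated secondary outcomes. It does not undermine the planned weight and waist comparisons. Nor should the change be described as having no downside: the stated gain depends on the quadratic shape holding for the arm difference. Categorical time removes that dependence but gives up the smoothing.

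**What to change.** In the long-term paragraph of Statistical Analysis, state that time is coded 0 at baseline, that the study-arm main effect is omitted, and that the time-by-arm and time-squared-by-arm terms are kept, so both arms share one baseline mean. Add that the resulting arm differences at 12 and 18 months will be reported with 95% intervals for all outcomes.

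Do not offer baseline as a covariate as an interchangeable alternative while the quadratic shape is kept. If the team doubts the quadratic, it can use categorical time with a common baseline mean and accept the lost smoothing.

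The cost is a sentence or two of analysis wording, with no new data and no change to trial conduct.

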While there is compelling evidence demonstrating the benefits of weight-loss interventions for both diabetic and pre-diabetic individuals, Hispanic participants typically lose less weight than non-Hispanic white participants, even in successful trials. Furthermore, most large randomized trials have selected only adherent individuals, using strict filtering criteria that screen out individuals generally considered poor candidates for retention.⁴⁶⁻⁴⁹ Many of the successful interventions tested in clinical trials may be too resource-intensive for implementation in community settings⁴⁰ and often include costly incentives, meal replacement products⁴⁰ or home visits.⁵⁰

The current study will be implemented in a federally qualified health center (the Virginia Garcia Memorial Health Center, VGMHC) primarily serving low-income Hispanic patients. We will compare the efficacy of a culturally competent group intervention targeting Hispanic women with impaired glucose regulation (diabetic and prediabetic patients), contrasting it with a usual care control condition. The intervention we will be testing is modeled on an intervention program for obese Mexican-American women we previously conducted at KPNW CHR.¹⁴ Our study will assess the cost of the intervention within the context of the clinical trial, and will assess the feasibility and cost of implementation in the absence of research support.

To ensure that this intervention is viable, sustainable, and able to be disseminated, and not merely a one-time research project, the program will be conducted by Virginia Garcia clinic staff, with training, supervision and support, and a minimum of “scaffolding” provided by the research team. Following the clinical trial, and at the request of VGMHC we will assess the sustainability and cost of the intervention as delivered by the interventionists without support from research staff.

Aims

1. Assess short (6-month) and long-term (12- and 18-month) changes in body weight and waist circumference in women in the intervention group compared to an enhanced usual-care control group

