 - o 2-h post glucose level on the 75-g oral glucose tolerance test $\geq 140-199$ mg/dL (7.8-11.0 mmol/L)
 - o Hemoglobin HbA1c ≥ 5.7
 - o Diagnosis of diabetes in patient's medical chart

- Diagnosis of prediabetes in patient's medical chart
- Residing in the Portland metropolitan area, and having no plans to leave the area in the next 18 months.
- Willing and able to attend the 26-weekly group meetings and 6 monthly group meetings.
- Willing to accept random assignment to the active intervention or enhanced usual care control.
- Clearance by the patient's VGMHC primary care physician to participate in the intervention.

Exclusion criteria

- Treatment for cancer in the past two years (excluding non-melanoma skin cancers).
- Having conditions that require limitation of physical activity or that would be contraindicated for the DASH diet patterns.
- Taking weight-loss medication currently or within the past 6 months.
- Current or recent (\leq 12 months) pregnancy, breastfeeding, or planning pregnancy in the next 18 months.

Recruitment

After attending an explanatory session as part of the informed consent process, each participant will sign the IRB-approved, written, bilingual, study consent prior to being enrolled in the study. The consent form will describe the purpose of the study, the requirements for participation, and the potential benefits and risks. It will also document that participation is voluntary, that it may be terminated by the participant at any time, and that decision to participate will not affect the clinical care received at VGMHC.

Potentially eligible patients from VGMHC will be identified through a review of the electronic medical record and through direct physician referral. Potentially eligible patients will be mailed a written description of the study and a consent form to review. Recruitment materials will be provided in both Spanish and English. Interested women will be invited to call the research center for more information, and those who are not interested in participating will be able to decline by telephone or by mail. Those who do not respond to the mailing may be called by a bilingual project staff member and asked about their interest in the study.

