After the completion of the first six months of weekly intervention sessions, participants will attend monthly group sessions and will also interact with each other weekly by telephone. The monthly group sessions and weekly telephone contacts constitute a weight-maintenance phase which will help maintain self-management behaviors started during the initial intervention. The self-management behaviors include setting weekly behavioral goals and developing specific action plans to achieve those goals, social disclosure of these goals and plans, and scheduled accountability for evaluating the outcomes of these plans.

The structure of these monthly, one hour and-a-half group sessions of the maintenance phase will be similar to the initial weight loss sessions, starting with a weigh-in and reporting to the group regarding the outcome of their weight management efforts since the last group session. The session leaders will then lead a discussion focused on a selected self-management strategy such as environmental modification, stimulus control, or social contracting, with illustrations taken from the participants' experience. There will also be a presentation on a topic recommended by participants at previous meetings, emphasizing managing ongoing challenges of making appropriate food choices and managing total energy intake, motivation, and resistance training.

Motivation for attending the monthly group sessions are social support from other group members, new information on nutrition presented by group leaders, and advice from peers and group leaders. The importance of attending the monthly maintenance meetings will be emphasized during the final 4 weekly weight-loss sessions with encouragement for participants to make a commitment to the group to return to the monthly meetings.

Participants will be asked to establish a telephone support net for which each participant will call one other participant between group meetings. This telephone contact, which will be promoted as a transition aide and as an essential part of the weight-loss maintenance program, will be introduced 2 weeks before the end of the weekly sessions. Participants will be encouraged to contact each other according to a mutually agreed upon schedule for brief (5-10 minute) supportive telephone conversations. The network will provide ongoing social support between the monthly group sessions.

Dietary, Exercise and Behavioral Recommendations

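### The long-term growth curve leaves the time-squared by arm term unstated and names no 12- or 18-month contrast, so two of the three primary time points have no defined estimate

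*Combined protocol and SAP*

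**What the plan says.** Aim 1 reads "Assess short (6-month) and long-term (12- and 18-month) changes in body weight and waist circumference in women in the intervention group", in comparison with enhanced usual care. Research Design repeats the three time points: "The primary aims of the intervention will be to reduce body weight and waist circumference at 6, 12, and 18 months".

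Statistical Analysis gives the 6-month comparison its own regression of change on baseline value and arm. For the long term, "we will use multilevel modeling to examine the trajectory of the outcomes across baseline, 6, 12, and 18 months". The terms are given as "time, study arm, and the time by study arm interaction are the independent variables. Quadratic models will be fit to the data", because "it is anticipated that the change over time will not be linear throughout the 18 month period". The same approaches are to serve for "the short-term and long-term effects of the intervention on other outcomes: waist circumference" and the remaining outcomes.

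The section does not say whether the squared term is common to both arms or arm-specific. It names no coefficient, joint test or fitted difference at 12 or 18 months as the long-term result.

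On contact with participants, Eligibility asks that they be "Willing and able to attend the 26-weekly group meetings and 6 monthly group meetings", and Weight Loss Intervention says "After the completion of the first six months of weekly intervention sessions, participants will attend monthly group sessions".

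**The concern.** Two of the three primary time points are reached only through a fitted curve, and the text permits two curves. If time-squared interacts with arm, the arm difference is a parabola in time. If only linear time does, the arm difference is forced to be a straight line, although the plan itself expects change that is not linear. Either curve also offers two candidate results at a visit: the difference in fitted change from baseline, or the fitted gap between arms. These are not the same number.

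The shape of the true difference is not fixed by the documents. Contact drops from weekly to monthly at 6 months, and six monthly sessions, if consecutive, end at about 12 months. The difference could peak at 6 months, peak at 12, hold or build slowly. Any bend that the curve cannot follow moves information from one visit to another, and whoever chooses the reading after seeing the data also chooses the 12-month answer.

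**Working it through.** **Inputs.** From the documents: visits at 0, 6, 12 and 18 months; 200 women in two equal arms, taken as 100 per arm. Assumed, because the documents give no effect size or SD: the true arm differences d6, d12, d18 in kg (d0 = 0 by randomisation); between-person SD 15 kg; slope SD 0.15, 0.25 or 0.4 kg/month crossed with residual SD 2, 2.5 or 3 kg; complete data. The plan states no figure on this point to reproduce.

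**Method.** Generalised least squares on the four arm differences with random intercept and slope. With equal spacing and complete data the fitted values do not depend on the SDs; only coverage and power do.

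**Reading A, time-squared by arm included.** A parabola misses only the third difference, c = 3·d6 − 3·d12 + d18. Fitted values equal truth plus c/20 at baseline, 3c/20 at 12 months and −c/20 at 18 months. Fitted change from baseline is therefore:
- 12 months: d12 + c/10 = 0.3·d6 + 0.7·d12 + 0.1·d18
- 18 months: d18 − c/10 = −0.3·d6 + 0.3·d12 + 0.9·d18

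The error has the same size at both visits and opposite signs.

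**Reading B, only linear time by arm.** With centred times −9, −3, 3, 9, the slope is (−3·d6 + 3·d12 + 9·d18)/180. Hence:
- 12-month change = 12 × slope = −0.2·d6 + 0.2·d12 + 0.6·d18
- 18-month change = 18 × slope, identical to reading A
- 12-month gap = mean + 3 × slope = 0.2·d6 + 0.3·d12 + 0.4·d18
- baseline gap = mean − 9 × slope = 0.4·d6 + 0.1·d12 − 0.2·d18

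| True 6/12/18 | c | A: change 12 | A and B: change 18 | B: change 12 | B: gap 12 | B: baseline gap |
|---|---|---|---|---|---|---|
| -4/-3/-2 | -5 | -3.5 | -1.5 | -1.0 | -2.5 | -1.5 |
| -4/-4/-4 | -4 | -4.4 | -3.6 | -2.4 | -3.6 | -1.2 |
| -4/-2/-1 | -7 | -2.7 | -0.3 | -0.2 | -1.8 | -1.6 |
| -2/-3/-4 | -1 | -3.1 | -3.9 | -2.6 | -2.9 | -0.3 |
| -4/-5/-3 | 0 | -5.0 | -3.0 | -2.0 | -3.5 | -1.5 |
| -3/-4/-3 | 0 | -4.0 | -3.0 | -2.0 | -3.0 | -1.0 |
| -2/-4/-3 | +3 | -3.7 | -3.3 | -2.2 | -2.8 | -0.6 |

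**Size of error.** Reading A, change: 0 to 0.7 kg at each visit. Reading B, 12-month change: 0.4 to 3.0 kg. Reading B, 12-month gap: 0.1 to 1.5 kg. The true baseline gap is zero in every row, so the last column is an artefact of the straight line.

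**Coverage of the 95% interval for change at 12 months.** Reading A: 67–88% for -4/-2/-1, 81–91% for -4/-3/-2, and 90–95% for the gradual and 12-month-peak shapes. Reading B: 0–46%, except 80–92% for the gradual shape.

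**Power at 18 months, curve against adjusted visit contrast** (smallest to largest SDs):
- -4/-3/-2: 80% against 95%, to 25% against 40%
- -4/-2/-1: 9% against 44%, to 6% against 14%
- -4/-4/-4: about 100% for both, to 87% against 92%
- -2/-3/-4: 92% for both at the largest SDs
- -4/-5/-3: 73% against 72% at the largest SDs
- -2/-4/-3: 81% against 72% at the largest SDs; the curve is higher because it overstates the effect

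With 80 per arm (20% loss, assumed), -4/-3/-2 gives 70% against 90%, to 21% against 33%.

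**Price of the visit model.** At the central SDs (0.25 and 2.5), standard errors of the 12-month change are 0.636 (reading A) and 0.653 (visit contrast); at 18 months, 0.794 and 0.807. Squared ratios are 1.05 and 1.03.

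**The case against.** The strongest reply is that a quadratic model naturally means squared time wherever time appears, including inside the interaction. That stands: it fits the stated purpose of comparing non-linear trajectories, and reading B requires expanding time in the main effect but not in the interaction. A reader might infer that the plan commits to reading B and that its 12-month result will be wrong by 2 kg or more. The documents do not support this. The term is unstated, not excluded, and even under B an error of 2 kg or more arises for the change estimate in only three of the seven assumed profiles.

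A second reply is that the fitted 12-month gap under B misses by much less than the change does. That is also true, but it is a weak rescue. Aim 1 speaks of changes, and the same model puts a false gap between randomised arms at baseline. The gap also carries the whole between-person variance: with an SD of 15 kg, √(2 × 15²/100) = 2.1 kg before any other variance, so its standard error is above 2 kg.

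A third reply is that a growth curve is an accepted method and that detection is safe. Under reading A the joint 2-df arm-by-time test has about 90% power or more for all seven profiles at 100 per arm, so it would be wrong to infer that a long-term effect would be missed altogether. What remains is that a joint test does not estimate the 12- and 18-month differences that the aim names, and that reading A still biases both for five of the seven shapes.

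**Conclusion.** The point holds as a gap in specification with a better method readily available. The 12- and 18-month parts of the primary aim have no named estimate, and the model behind them can be read in two ways. On the more natural reading the harm is moderate: 0 to 0.7 kg in the change at each visit, with 18-month power lost for shapes that peak at 6 months and then decline, and little or none lost, or some gained, for others. On the less natural reading the 12-month change can be off by 0.4 to 3.0 kg. The 18-month change is the same on both readings, so adding the squared interaction does not repair it.

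The algebraic weights need only equal spacing, complete data and a random intercept and slope. The kilogram figures, coverage and power rest on assumed profiles and SDs. The 6-month result is unaffected because it has its own regression. This should be fixed before analysis.

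**What to change.** In Statistical Analysis, make the main long-term model one with visit as a category (6, 12, 18 months), visit-by-arm terms and baseline adjustment: the baseline value as a covariate, as in the 6-month regression, or baseline means constrained equal across arms. Name the adjusted arm differences at 12 and 18 months, for weight and for waist, as the long-term estimates. Keep the quadratic curve as a descriptive trajectory analysis and state that time-squared by arm is included.

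If the sponsor prefers to keep the curve as the main model, the least that is needed is to state the squared interaction and name the 12- and 18-month contrasts. That removes the ambiguity but leaves the 0 to 0.7 kg shape error.

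The change is one of wording; the four visits are already planned. It adds a few parameters with about 200 women. If the quadratic-by-arm curve were exactly right, the visit contrasts would have about 5% more variance at 12 months and 3% more at 18 months at the central SDs (2–7% and 1–6% over the SD range).
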